4.1 Rationale for study design

This study will evaluate the safety and efficacy of two concentrations of SAF312 twice daily for 12 weeks in the treatment of CICP following refractive or cataract surgery. The aim is to evaluate the treatment effect of SAF312 compared to placebo, and to determine the appropriate concentration to carry forward for further development.

The active and placebo IMPs will be presented in identical packaging to ensure no bias to the study results due to knowledge of the treatment assignment. Due to the difference in appearance of SAF312 eye drops vs placebo eye drops (milky white vs clear, respectively), sites will be required to have an unblinded staff member to manage drug dispensation, drug accountability, as well as collection of adverse events or subject reports of product comments/complaints. All other site staff and Sponsor staff will be blinded to treatment assignments. To ensure masking of subjects to their treatment assignment, no subject will receive both placebo and active treatment so no change in appearance of the test article will be noticeable by a particular subject. Subjects may be informed that their study treatment may appear cloudy or white, but must not be informed about the specific identity of the treatments based on differences in appearance.

A 12-week observation period prior to randomization is included as a method to confirm the chronicity of their ocular pain, observe trends in the subject's pain occurrences (
), and to observe behaviors with artificial tears and rescue medications prior to receiving randomized treatment. This observation period confirms the selection of

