6.1 Study treatment

6.1.1 Investigational and control drugs

SAF312 will be supplied to the subject as ocular eye drops to be administered into the conjunctival sac. Subjects will self-administer their first dose at the clinical study site in the presence of an *unblinded* site personnel prior to completion of Visit 2. Subsequent drops will be administered at home by subjects.

Sponsor-qualified medical personnel will be readily available to advise on trial related medical questions or problems. Any questions related to the identity of the IMP must be addressed by an *unblinded* site personnel.

Table 6-1 Inv	estigational and	control drug
---------------	------------------	--------------

Investigational/ Control Drug	Pharmaceutical Dosage Form	Route of Administration	Presentation	Sponsor (global or local)
SAF312 15 mg/ml	eye drops, suspension	topical ocular	double blind opaque droptainer	Novartis Global
SAF312 5 mg/ml	eye drops, suspension	topical ocular	double blind opaque droptainer	Novartis Global
SAF312 Placebo	eye drops, suspension	topical ocular	double blind opaque droptainer	Novartis Global

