6.4 Treatment blinding

Subjects, investigator staff, persons performing the assessments, study monitors and Clinical Trial Team (CTT) will remain blind to the identity of the treatment from the time of randomization until database lock, using the following methods: (1) Randomization data are kept strictly confidential until the time of unblinding and will not be accessible by anyone else involved in the study with the following exceptions: unblinded site personnel will be required for initial dose administration, and discussions with subjects that may contain unblinding information (2) the identity of the treatments will be concealed by the use of study treatment that are all identical in packaging, labeling, and schedule of administration.

Unblinding of the investigator may occur in the case of subject emergencies and at the conclusion of the study.

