6.7 Preparation and dispensation

Each study site will be supplied with study drug in packaging as described under investigational and control drugs (Section 6.1.1).

A unique medication number is printed on the study medication label.

Investigator staff will identify the study medication kits to dispense to the subject by contacting the IRT and obtaining the medication number(s). The study medication has a 2-part label (base plus tear-off label), immediately before dispensing the medication kit to the subject, site personnel will detach the outer part of the label from the packaging and affix it to the source document.

An *unblinded* site personnel will instruct the subject on proper drug storage and use, and will dispense the assigned medication to the subject, prior to instillation of the first dose of study medication at the site.

As per Section 4.6, during a Public Health emergency as declared by Local or Regional authorities i.e. pandemic, epidemic or natural disaster, that limits or prevents on-site study visits, delivery of IMP directly to a subject's home may be permitted (if allowed by Local or Regional Health Authorities and Ethics Committees as appropriate) in the event the Investigator has decided that an on-site visit by the subject is no longer appropriate or possible, and that it is in the interest of the subject's health to administer the study treatment even without performing an on-site visit. The dispatch of IMP from the site to the subject's home remains under the accountability of the Investigator. Each shipment/provisioning will be for a maximum of 1 month supply. In this case, regular phone calls or virtual contacts (e.g., every 2 weeks or more frequently if needed) will occur between the site and the subject for instructional purposes, safety monitoring, investigation of any adverse events, ensuring subjects continue to benefit from treatment, and discussion of the subject's health status until the subjects can resume visits at the study site.

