8.3 Efficacy

8.3.1 Pain Severity and Frequency Visual Analog Scales

The pain severity Visual Analogue Scale (VAS) is to be completed through an electronic diary by the subject at the Screening Visit, and thereafter every evening (before bed during the observational period, and before their evening dose of study medication during the study treatment period). The subject will provide a score for severity of their ocular pain over the past 24 hours by putting a vertical mark on the horizontal scoring line. The severity scoring line utilizes the anchors of 'No Pain' to 'Very Severe' pain.

The Pain Frequency Visual Analogue Scale (VAS) is to be completed through an electronic diary by the subject at the Screening Visit, and thereafter every evening (before bed during the observational period, and before their evening dose of study medication during the study treatment period). The subject will provide a score for frequency of their ocular pain over the past 24 hours by putting a vertical mark on the horizontal scoring line. The frequency scoring line utilizes the anchors of 'Rarely' to 'All the Time'.

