8.5.1.6 Mitigation of Placebo Response Training Video and Pain Assessment Knowledge Check

At Screening Visit (Visit 1): Upon completion of ICF but before starting the use of ePRO device, the subject will use the study tablet device, personal mobile device, laptop, or tablet to watch a video regarding placebo response mitigation.

After completing the video, a printed copy of the Pain Assessment Knowledge Check will be given to the subject to have him/her complete the questions in order to check their level of

understanding of the video content. Site staff should review the responses with the subject and answer any questions they may have regarding incorrect responses or the information as a whole.

At Baseline/Randomization Visit (Visit 2): if the subject meets criteria for randomization, the study subject is expected to watch the Video once more BEFORE they leave the clinic. The Pain Assessment Knowledge Check can be optional for any subject who had completed the Knowledge Check already during Visit 1 (Screening).

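### The only description of the drops that Protocol 4.1 lets sites give subjects fits the active arms and not the clear placebo: an avoidable cue to the arm, of unknown size and low severity

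*Protocol*

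**What the plan says.** Protocol 4.1 explains why each site needs an unblinded staff member: "Due to the difference in appearance of SAF312 eye drops vs placebo eye drops (milky white vs clear, respectively"). The same paragraph then says what subjects may hear: "Subjects may be informed that their study treatment may appear cloudy or white, but must not be informed about the specific identity of the treatments" on the basis of how the products differ. Neither document gives any other appearance wording for subjects.

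The plan has several safeguards. Packaging and labelling are identical (Protocol 4.1 and 6.4), the droptainers are opaque (Table 6-1), and no subject receives both products (4.1). Section 6.4 adds that "unblinded site personnel will be required for initial dose administration, and discussions with subjects that may contain unblinding information". SAP Table 5-1, item OTH09, lists as a deviation the case where a description of appearance reveals the treatment; subjects with that deviation stay in all analysis sets.

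The first dose is taken at the site. After that, "Subsequent drops will be administered at home by subjects" (Protocol 6.1.1), twice daily for 84 days (6.1.3 and 6.1.4). The primary endpoint, change in weekly mean pain severity VAS at Week 12, comes from a daily diary: "The subject will provide a score for severity of their ocular pain over the past 24 hours" (8.3.1).

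**The concern.** The permitted sentence gives the subject an outside reference. Someone told to expect cloudy or white drops who then sees clear ones has a mismatch to interpret; someone on active treatment has none. The cue therefore points at one arm.

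A placebo subject who suspects placebo may report less improvement, and on a self-reported endpoint that would look like a drug effect. The plan already takes expectation seriously: subjects are asked "to watch a video regarding placebo response mitigation" at Visit 1 and again at Visit 2 (Protocol 8.5.1.6). Active-only wording works against that precaution. Nothing in either document plans to record subjects' treatment guesses, so unmasking could not be measured afterwards.

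**Working it through.** **1. Do the safeguards remove the cue?** Set side by side:

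- Opaque bottles and identical packaging hide the liquid in the container. They do not hide a drop that the subject instils.
- Giving each subject only one product prevents a change in appearance within a subject. It does not prevent comparison with a description the subject has been given.
- The ban on disclosing treatment identity, and OTH09, address statements that reveal the arm. The sentence in 4.1 is expressly permitted, so OTH09 would not catch it.

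The cue remains wherever the sentence is used.

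**2. The plan's own power figure.** Inputs from Protocol 12.8.1: 50 per arm, difference 15 mm, SD 23 mm, two-sided 5% adjusted for two comparisons.

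- SE = 23 × √(2/50) = 4.60 mm; noncentrality = 15/4.60 = 3.26.
- Two-sample noncentral t at two-sided 0.025: 83.6%.
- Dunnett critical value (correlation 0.5, 147 df) of 2.234: 84.7%.
- The plan states about 83%, so its inputs reproduce.

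**3. Sensitivity of the primary test to any unmasking of placebo.** This is not the effect of the sentence. Assume no true effect and an average shift of b mm in the placebo arm towards less improvement. The two t statistics share the placebo arm, and each is displaced by b/4.60. The table gives the chance that at least one exceeds +2.234, that is, a false finding in favour of SAF312 (numerical integration).

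| b (mm) | chance |
|---|---|
| 0 | 2.5% |
| 0.25 | 2.9% |
| 0.5 | 3.2% |
| 1.0 | 4.2% |
| 1.25 | 4.7% |
| 1.5 | 5.3% |
| 1.75 | 6.0% |
| 2.25 | 7.5% |

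The chance doubles to 5% at b = 1.37 mm. With the other SDs in Table 12-1, it does so at 1.19 mm (SD 20) and 1.01 mm (SD 17).

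**4. What the sentence might add, all inputs assumed.** Let each subject who infers placebo report 5 mm less improvement. Then b = (share inferring placebo without the sentence + share the sentence adds) × 5 mm.

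- Share without the sentence 0%, adding 0, 5, 10 or 20 points: b = 0, 0.25, 0.5, 1.0; chance 2.5%, 2.9%, 3.2%, 4.2%.
- Share without the sentence 25%, adding 0, 5, 10 or 20 points: b = 1.25, 1.5, 1.75, 2.25; chance 4.7%, 5.3%, 6.0%, 7.5%.
- Largest increment: 7.45 − 4.71 = 2.7 percentage points.
- Small additions matter little: from 0%, adding 1 or 2 points (b = 0.05 or 0.10) gives 2.57% or 2.64%.
- The added share could be negative if the replacement wording prompts more guessing. From 25%, taking 5 points away (b = 1.0) gives 4.2% against 4.7%.

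**The case against.** The sentence is permissive twice over: sites need not say it, and it says only how the drops may look. It does not say that every treatment is cloudy or that clear means placebo, and neutral wording is not barred. It sits in a rationale section; the operative blinding section, 6.4, does not repeat it. Table 6-1 labels the placebo a suspension like the active product. The consent form is a separate document, and it may already contain uniform wording. All of this stands, and it keeps the severity low.

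It is also fair that wording which mentions both appearances is not shown to be better. The current text never tells subjects that two appearances exist; a neutral sentence tells everyone. The documents cannot settle which prompts less guessing. What remains is that the current description fits only the active arms, whereas a common sentence points to no arm, and giving no description avoids both problems.

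Two stronger readings are tempting. A reader might infer that unblinded staff could use the sentence selectively, because in Protocol 6.7 an unblinded person is the one of whom it is said that "site personnel will instruct the subject on proper drug storage and use, and will dispense the assigned medication to the subject". That passage concerns storage, use and dispensing, and nothing says who delivers the appearance sentence, so this is speculation. A reader might also infer from SAP 2.1.1.1, which describes active and placebo as looking the same, that the SAP contradicts the protocol about the liquid. Its mention of the containers suggests that packaging is meant.

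**Conclusion.** The point holds as a low-severity wording fault. The white/clear difference, the active-only description, dosing at home and the self-reported endpoint are all in the text, and the listed safeguards do not remove the cue where the sentence is used.

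Its size is unknown. A reader might infer from the working that the blind is broken, or that the false-positive rate is inflated by up to 2.7 points. The documents support neither. They give no unmasking rate, no background share of subjects who would guess, and no shift in reported pain. The range from nil to 2.7 points follows from the assumed 5 mm, the assumed shares of 0% and 25%, and added shares that were not allowed to be negative. The 1.37 mm doubling point describes unmasking of placebo from any source, most of which could persist whatever sites say, because the drops look different. The effect of the sentence alone may be nil.

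**What to change.** In Protocol 4.1, remove the active-only description. Either give subjects no description of appearance or, if one is needed, use a single fixed sentence, identical for every subject in every arm, that covers both products; for example, that the drops may look clear, cloudy or white. Keep the ban on linking appearance to treatment. OTH09 already records breaches of masking through a description of appearance and can stay as it is.

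The cost is wording only: no extra staff, visits or data. The visible difference between the products remains, and a sentence covering both appearances tells all subjects that appearance may vary, which may prompt some guessing.

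Two clarifications, neither of which carries the point:

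- Reconcile Protocol 4.1, 6.4 and 10.1.1 on who collects adverse events. Section 4.1 gives the unblinded person "collection of adverse events or subject reports of product comments/complaints" without limiting this to reports that may reveal appearance, while 10.1.1 makes the investigator responsible for identifying adverse events.
- Reword SAP 2.1.1.1 so that sameness refers to packaging.

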4.2 Rationale for dose/regimen and duration of treatment

actions. The only requirement will be completion of eDiary data, and pain assessments.

Topical ocular administration of SAF312 eye drops in non-clinical studies has resulted in high ocular exposure with minimal systemic exposure, which is expected to enable ocular pain management while avoiding systemic side effects. In the FIH study CSAF312X2101, dose concentrations of 5 mg/ml, 15 mg/ml and 25 mg/ml (0.5%, 1.5% and 2.5%, respectively) were administered as a single drop 4 times daily in one eye of a subject for 7 days. A supra-therapeutic dose concentration of SAF312 eye drops was tested using the maximum feasible dose (MFD) of 25 mg/ml (2.5%) and administered 8 times daily for 7 days. In each evaluation, SAF312 was safe and well tolerated at single and multiple ocular doses, even up to supra-therapeutic dose concentration levels. Esthesiometry assessments also demonstrated the lack of any anesthetic effect of SAF312 eye drops when compared to Tetracaine topical ocular anesthetic drops.

In the proof-of-concept study for the treatment of acute ocular pain after PRK (photorefractive keratectomy) surgery, SAF312 at 25 mg/ml (2.5%) was administered 4 times daily (every 6 hours) for 72 hours. SAF312 was safe and well tolerated with no notable systemic or ocular adverse events, and no delay in wound healing. Systemic exposure of SAF312 was confirmed to be minimal (Cmax 2.40 ng/mL on Day 4) which is consistent with the lack of observed systemic adverse events.

An ocular PK study in rabbits was conducted to determine the tissue concentrations of SAF312 eye drop in selected ocular tissues and plasma following a single topical ocular administration in both eyes, at four different dose concentrations of SAF312 at 5 mg/ml, 10 mg/ml, 15 mg/ml and 25 mg/ml (0.5%, 1.0%, 1.5% and 2.5%, respectively). Concentrations of SAF312 in the cornea and conjunctiva were greater than ten times the IC₅₀ (estimate of the IC₉₀) for up to 12 hours post-instillation (12 hours was the end of the evaluation period). There was an approximate dose-proportionality for increase in SAF312 area under the curve (AUC) and Cmax in the cornea and conjunctiva, and Cmax between 5 mg/ml and 10 mg/ml, but less than dose-proportional above 10 mg/ml. There was also differentiation in exposure observed between 5 mg/ml and 10 mg/ml but no clear differentiation between 10 mg/ml and 15 mg/ml or 25 mg/ml.

In toxicology studies completed to date, no notable adverse events were identified after 2 weeks of topical ocular dosing. Likewise, no notable adverse in-life events were observed when SAF312 was administered up to a dose concentration of 25 mg/ml (2.5%) four times daily for 13 weeks.

Based on these data, the Phase 2 study includes dosing of SAF312 at concentrations of 5 mg/ml (0.5%, lowest feasible dose) and 15 mg/ml (1.5%, highest feasible dose) to ensure evaluation of the full range of possible concentrations, and evaluation of concentrations that have potential to reveal a dose response based on differentiated tissue exposure. With target tissue exposure concentrations remaining well above the estimated IC₉₀ for at least 12 hours, b.i.d. dosing has been selected as the dosing frequency.

Twelve weeks of exposure will allow for proper assessment of: 1) the efficacy of treatment response, 2) the safety of prolonged TRPV1 inhibition in the eye, and 3) the sustainability of the effect of the treatment (eg, no loss of effect over time). Both eyes will be treated with the IMP. Because it is difficult for subjects to clearly delineate pain from one eye or the other, treating both eyes will avoid confounding the data with pain that may not be addressed in the eye that does not receive treatment. There have been no safety concerns identified with the use of SAF312 eye drops, and the systemic exposure via topical ocular administration is very low, therefore dosing both eyes is not expected to pose additional safety risks to the subject.

Because PK has already been evaluated in both the FIH and the Phase 2a PRK (PoC) studies, PK is not planned as part of this Phase 2 study in patients with CICP. Plasma samples may, however, be collected ad hoc in cases of SAEs.

4.3 Rationale for choice of control drugs (comparator/placebo) or combination drugs

Currently, there is no standard of care for CICP. If pharmacological treatments are needed, treatments may include short-term off-label use of topical ocular steroids, or non-steroidal anti-inflammatory medications, or oral pain medications.

Subjects will be allowed to continue using medications needed to treat concurrent ocular conditions. The use of placebo (vehicle) as a comparator is therefore not considered to be an undue risk to the subjects enrolled in the trial. Moreover, since there is no standard of care for the treatment of CICP, the use of placebo as a comparator will allow for the establishment of the magnitude of change in the clinical endpoints that may be seen spontaneously during treatment, and therefore provide a better estimate of the true treatment effect of SAF312.

4.4 Purpose and timing of interim analyses/design adaptations

Not applicable.

4.5 Risks and benefits

As of yet there is no known benefit to receiving topical ocular SAF312 treatment for the Corneal Induced Chronic Pain (CICP) indication. The safety, tolerability and pharmacokinetics of SAF312 eye drops has been evaluated in two studies. A FIH Phase 1 study established the safety and tolerability of SAF312 eye drops when used at concentrations as high as 25 mg/mL (2.5%) up to 8 times per day, for 7 days, established the lack of an anesthetic effect, and revealed low systemic exposure of the drug. The PoC study in acute pain after PRK surgery confirmed the low systemic exposure and demonstrated efficacy of SAF312 eye drops in reducing post-operative pain compared to placebo when dosed 4 times per day for 3 days. In both studies, the adverse effects observed with oral dosing of SAF312 (eg, heat insensitivity, transient hyperthermia, autonomic dysreflexia in patients with spinal cord injury) were not observed. Together, these data support the anticipated safety and efficacy of SAF312 eye drops for the treatment of CICP. Because there is no standard of care for CICP, and treatment options for chronic pain are limited, SAF312 may provide a novel approach to address the current unmet need for patients in need of a chronic treatment for CICP.

Protocol No. CSAF312B12201

Any risks to subjects in this current study may be minimized by compliance with the eligibility criteria and study procedures, as well as close monitoring by the study staff.

When dosed orally, SAF312 resulted in autonomic dysreflexia in one subject with spinal cord injury. Even though systemic exposure with SAF312 is very low with topical ocular administration, due to the severity of this potential event, patients with spinal cord injury will be excluded from the study.

Patients will undergo certain ophthalmological procedures which are standard in clinical practice and ophthalmic clinical studies. The assessment of the ocular surface requires the use of fluorescein and lissamine vital dyes. As with any application of a substance to the ocular surface, the patient may have unknown hypersensitivities to the dyes. Any subject demonstrating a potential hypersensitivity reaction will receive appropriate medical care. To minimize any risks, the study and associated procedures will be carried out by experienced study staff under the supervision of the Principal Investigator.

Subjects enrolled in the study will be allowed to continue any current medications they may be prescribed to treat a concurrent or underlying ocular condition which avoids any risk of worsening of those conditions due to study requirements. Although subjects may receive placebo instead of active drug, the use of placebo is not considered a risk since it is the same formulation as the IMP but without the active ingredient. If patients receive inadequate treatment of CICP due to the use of placebo, patients will be allowed to use rescue medication to avoid any undue risk or suffering as a result of study requirements.

Given the minimal systemic exposure after topical ocular administration, and the lack of safety findings in non-clinical or clinical studies conducted to date, the foreseeable risks associated with SAF312 eye drops are considered low compared to the anticipated benefit for patients with CICP. There may be risks associated with the use of SAF312 which are unknown at this time.

